3.5 Location of laboratory and imaging facilities

[figure not shown]
The laboratory and imaging facilities for this study are both located on the 3rd floor of the BC Cancer Agency at [name].

4. Study design

Phase II, open-label, single-arm trial of patients with refractory mCRC treated with regorafenib (160 mg/day) and perindopril (4 mg/day).

This study will be conducted at the BC Cancer Agency (Vancouver Centre) only.

PARICCA trial design

Primary endpoint: Incidence of all grade toxicities for HFSR

Secondary endpoints: Incidence of (all grade) hypertension & toxicity; Severity of HFSR; Time course to development of worst grade (stage3) HFSR; Progression Free Survival.

Treat until progression, unacceptable toxicity, or withdrawal

During the study period, patients will undergo evaluations for safety and drug accountability every cycle. Drug safety will be monitored and evaluated continuously throughout the study, including a 30-day follow up period. Patients will continue on treatment until one of the following occurs (main criteria):

- Progressive Disease as defined by Response Evaluation Criteria in Solid Tumors (RECIST) criteria, version 1.1, or clinical progression
- Death
- Unacceptable toxicity
- Patient withdraws consent
- Treating physician determines discontinuation of treatment is in the patient's best interest
- Substantial non-compliance with the protocol

For the full list of criteria refer to section 5.2.1.

If in the Investigator's opinion, treatment with regorafenib is providing clinical benefit to a patient experiencing disease progression, the patient may continue treatment.

Justification of the design

47% of regorafenib treated patients in the CORRECT trial experienced HFSR of all grades, while 17% of regorafenib patients experienced grade 3 HFSR. All efforts need to be made to find new therapeutic combinations to reduce HFSR, as it causes a significant decrease in a patient's quality-of-life.

Although we are assuming that the co-administration of perindopril with regorafenib will mitigate HFSR symptoms, this may not be the case. If the HFSR is more severe with the addition of perindopril than with regorafenib alone, the study will be discontinued.

The choice of dosage and schedule to be used in this trial comes from data accumulated in previous phase III trials with regorafenib (CORRECT, CONCUR). The choice of dosage and schedule for perindopril is from the Coversyl monograph.

End of study

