If a subject experiences several toxicities and there are conflicting recommendations, the recommended dose adjustment which reduces the dose to the lowest level should be used.

Table 3 outlines dose adjustments for toxicities related to study drug except hand-foot skin reaction, hypertension and liver function test (ALT and AST) abnormalities. **Table 4** outlines the suggested dose reductions for HFSR while **Table 5** outlines suggested dose reductions for treatment-emergent hypertension. **Table 6** outlines the suggested dose reductions for ALT and/or AST increases related to study drug.

If reduction by more than two dose levels is required, treatment will be discontinued.

If a dose reduction has been performed, intra- subject dose re-escalation can be considered (up to the maximal 160 mg daily dose) at the discretion of the treating physician provided that the toxicity (ies) has resolved to baseline.

Table 3: Dose Modification/Delay for Toxicities Related to Study Drug (Except Hand Foot Skin Reaction, Hypertension, AST and ALT)^a

Grade of Event (CTCAE version 4.03)	Dose Interruption	Dose Modification	Dose for Subsequent Cycles
Grade 0-2	Treat on time	No change	No change

Phase II Study of Perindopril and Regorafenib in mCRC (PARICCA)

Grade 3	Delay until \leq Grade 2 ^b	Reduce 1 dose level	If toxicity remains \leq Grade 2, dose re-escalation can be considered at the discretion of the treating investigator. If dose is re-escalated and toxicity (\geq Grade 3) recurs, institute permanent dose reduction.
Grade 4	Delay until \leq Grade 2 ^b	Reduce by 1 dose level. Permanent discontinuation can be considered at treating investigator's discretion.	

a Excludes alopecia, non-refractory nausea/vomiting, non-refractory hypersensitivity, non clinical significant and asymptomatic laboratory abnormalities.

b If no recovery after a 4-week delay, treatment will be permanently discontinued.

In addition to these recommended dose modifications, subjects who develop diarrhea, mucositis, anorexia or other events predisposing to fluid loss or inadequate fluid intake should be carefully monitored and rehydrated as clinically necessary. This is in order to minimize the risk of postural hypotension and renal failure.

Skin Toxicity Grade (according to CTCAE version 4.03 "Palmar-plantar erythrodysesthesia syndrome")	Occurrence c	Suggested Dose Modification c

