7.5 Safety

Although we are assuming that the co-administration of perindopril with regorafenib will mitigate HFSR symptoms, this may not be the case. Grade 3 HFSR rate will be evaluated after the first 10 patients have completed at least one cycle of regorafenib. If a significantly higher rate of grade 3 HFSR is seen in these first 10 patients i.e. Grade 3 is seen in more than 5 out of the 10 patients, the study will be discontinued.

Safety variables for **regorafenib** are as follows: adverse events, laboratory changes (hematology, clinical chemistry and clinical urinalysis), changes in vital signs (blood pressure, heart rate, respiratory rate, temperature) and electrocardiogram (ECG). These will be measured as per standard of care for regorafenib, as per study schedule (Table 7). See more details from product monograph below.

Phase II Study of Perindopril and Regorafenib in mCRC (PARICCA)

Safety variables for **perindopril** can be obtained from the COVERSYL® Product Monograph. The most frequent adverse reactions observed with perindopril are: cough, dizziness, headache, asthenia, gastro-intestinal disorders (abdominal pain, nausea, dyspepsia). The most serious adverse reactions are: hypersensitivity reaction (angioedema), renal dysfunction (in high risk patients), pancreatitis, blood disorders (pancytopenia, agranulocytosis, and thrombocytopenia). During the long-term safety assessment in heart failure patients, the severe adverse events occurring with the highest frequency were angina pectoris and orthostatic hypotension. The most severe drug reactions from post-marketing experience were pancreatitis and blood disorders (pancytopenia, agranulocytosis, and thrombocytopenia).

More detailed safety variables from the regorafenib monograph include:

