Regorafenib has been associated with an increased incidence of electrolyte abnormalities (including hypophosphatemia, hypocalcemia, hyponatremia and hypokalemia) and metabolic abnormalities (including increases in thyroid stimulating hormone, lipase and amylase). The abnormalities are generally of mild to moderate severity, not associated with clinical manifestations, and do not usually require dose interruptions or reductions. It is recommended to monitor biochemical and metabolic parameters during regorafenib treatment and to institute appropriate replacement therapy according to standard clinical practice if required. Dose interruption or reduction, or permanent discontinuation of regorafenib should be considered in case of persistent or recurrent significant abnormalities.

Since drugs with anti-angiogenic properties may suppress wound healing, treatment with regorafenib should be stopped at least 2 weeks prior to scheduled surgery. The decision to resume regorafenib after surgery should be based on clinical judgment of adequate wound healing. Regorafenib should be discontinued in patients with wound dehiscence.

Regorafenib may decrease heart rate. Caution should be observed in patients with a low heart rate at baseline (< 60 beats per minute), a history of syncope or arrhythmia, sick sinus syndrome, sinoatrial block, atrioventricular (AV) block, ischemic heart disease, or congestive heart failure.

Patients with a history of ischemic heart disease should be monitored for clinical signs and symptoms of myocardial ischemia. In patients who develop new or acute onset cardiac ischemia and/or infarction regorafenib should be withheld until resolution. The decision to re-initiate regorafenib therapy should be based on careful consideration of the potential benefits and risks of the individual patient. Regorafenib should be permanently discontinued if there is no resolution.

Phase II Study of Perindopril and Regorafenib in mCRC (PARICCA)

Regorafenib should be permanently discontinued in patients who develop gastrointestinal perforation or fistula.

Treatment with regorafenib should be stopped in patients with severe or life threatening hemorrhage. Patients receiving warfarin should be closely monitored.

For patients with observed worsening of liver function tests, dose modification (interruption, reduction) or discontinuation of regorafenib is recommended.

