In case of unexplained respiratory symptoms such as non-productive cough, dyspnea, crackles, or radiological pulmonary infiltrates, regorafenib should be discontinued until further pulmonary investigation excludes interstitial lung disease and pneumonitis.

Patients with severe hepatic impairment will be excluded. Closely monitor patients with any hepatic impairment for adverse reactions, discontinuation of regorafenib, along with control of hypertension and supportive medical management of other symptoms is recommended.

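### Section 7.5 and Table 3 give different instructions for gastrointestinal perforation or fistula and for wound dehiscence, and nothing says which prevails

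*Combined protocol and SAP*

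**What the plan says.** **Section 7.5 (Safety).** This text is introduced with "More detailed safety variables from the regorafenib monograph include". It then gives three instructions that do not depend on grade:

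- Perforation or fistula: "Regorafenib should be permanently discontinued in patients who develop gastrointestinal perforation or fistula".
- Dehiscence: "Regorafenib should be discontinued in patients with wound dehiscence".
- Unexplained respiratory symptoms or pulmonary infiltrates: "regorafenib should be discontinued until further pulmonary investigation excludes interstitial lung disease and pneumonitis".

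**Section 6.4.2, Table 3.** The title sets the scope: "Dose Modification/Delay for Toxicities Related to Study Drug (Except Hand Foot Skin Reaction, Hypertension, AST and ALT". Footnote a narrows it: "Excludes alopecia, non-refractory nausea/vomiting, non-refractory hypersensitivity, non clinical significant and asymptomatic laboratory abnormalities". At Grade 0-2 the table makes no interruption and no dose change. At Grade 3 it delays until Grade 2 or lower and then resumes one dose level down, with re-escalation possible. At Grade 4 it has the same delay, then: "Reduce by 1 dose level. Permanent discontinuation can be considered at treating investigator's discretion". The only permanent stop that the table makes mandatory is failure to recover after a four-week delay (footnote b).

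**Sections 4 and 5.2.1.** After its main stopping criteria, Section 4 adds: "For the full list of criteria refer to section 5.2.1". Section 5.2.1 names severe allergic reactions and certain bleeding events. It does not name perforation, fistula, dehiscence or lung toxicity. It does have two general clauses that rest on the investigator's judgement, one on harm from continuing and one on sufficiently serious adverse reactions.

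**The concern.** A drug-related perforation, fistula or dehiscence falls under both Section 7.5 and Table 3, and the two do not agree. Section 6.1 sends sites to Section 6.4 for dose modification and to Section 5.2 for stopping, and it does not mention Section 7.5. A site working from the dose table could therefore continue or resume regorafenib in a patient for whom Section 7.5 says it should be stopped. The protocol's section on expected adverse events lists perforation or fistula among the most serious reactions to regorafenib. Section 11.1 asks for strict adherence to all specifications, which is not possible where two of them differ.

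What is at stake is patient safety and uniform conduct, not the statistical operating characteristics of the trial.

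**Working it through.** No figure in the plan bears on this point, so there is nothing to recompute. The check is a comparison of passages.

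**Step 1: does Table 3 reach these events?** Its title excepts only hand-foot skin reaction, hypertension and AST/ALT. Footnote a removes only alopecia, some nausea, vomiting and hypersensitivity, and minor laboratory findings. Perforation, fistula, dehiscence and lung events are in neither list. Table 3 therefore applies whenever the event is judged related to study drug. The lead-in to the dose modifications sets that threshold low, because a possible relation is enough.

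**Step 2: compare the instructions.**

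| Event (drug-related) | Section 7.5 | Table 3, Grade 0-2 | Table 3, Grade 3 | Table 3, Grade 4 |
|---|---|---|---|---|
| Perforation or fistula | Permanent stop, any grade | Continue, no change | Delay, resume one level lower | Delay, reduce one level; permanent stop optional |
| Wound dehiscence | Stop, any grade; permanence not stated | Continue, no change | Delay, resume one level lower | Delay, reduce one level; permanent stop optional |
| Unexplained respiratory symptoms | Hold until interstitial lung disease and pneumonitis are excluded | Continue, no change | Delay until Grade 2 or lower | Delay until Grade 2 or lower; permanent stop optional |

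- *Perforation or fistula.* The instructions differ at every grade. At Grade 0-3 they cannot both be followed as written. At Grade 4 a site that stops permanently satisfies both, and a site that reduces and resumes satisfies only Table 3.
- *Dehiscence.* The pattern is the same but slightly softer, because Section 7.5 does not say the stop is permanent.
- *Respiratory symptoms.* The clash is at Grade 1-2: hold against continue. At Grade 3-4 both passages interrupt, but the restart conditions differ: a diagnosis excluded in one, recovery to Grade 2 or lower in the other.

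**Step 3: does any passage settle it?** Section 6.4.2 has a tie-break that takes the lowest recommended dose level. It is written for a patient with several toxicities whose recommendations conflict, not for one toxicity under two rules. No other text ranks Section 7.5 against Table 3.

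**Step 4: where does Section 5.2.1 stand?** It neither names the events nor tells a site to continue. Its two judgement clauses can cover all of them. It also leaves out stops that other tables do mandate, such as Grade 4 hypertension (Table 5), Grade 4 AST/ALT (Table 6) and a third Grade 3 hand-foot skin reaction (Table 4). Its silence here follows that general pattern.

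**Likely origin.** Section 6.4.2 says that its dose-modification text comes from the CONCUR protocol, and Section 7.5 says that its text comes from the product monograph. The two appear not to have been harmonised.

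**The case against.** The best case on the other side is that both passages are guidance. Section 6.4.2 says that doses may be delayed or reduced, and the text after Table 3 calls its content recommended modifications. Section 7.5 says *should*, in text carried over from the monograph. Nothing in Table 3 forbids a site from stopping, and an investigator who had read Section 7.5 would probably use the judgement clauses of Section 5.2.1 and withdraw the patient.

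Much of this stands. It means that Section 7.5 cannot be said to *require* discontinuation, and that at Grade 4 the two passages can both be satisfied. It does not remove the difference. If both are recommendations, neither outranks the other, and for the same Grade 2 or 3 fistula one recommends a permanent stop while the other recommends continuing or resuming. The judgement clauses permit withdrawal, but they do not tell a site which of the two texts to follow.

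A reader might also infer that Section 5.2.1, being called the full list, contradicts Section 7.5 or directs a site to keep the drug going. The documents do not support that: the list is silent on these events and its general clauses can take them in.

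A reader might also give the lung rule the same weight as the other two. It is a temporary, conditional hold, so its absence from a list of withdrawal reasons is no contradiction. Its Grade 1-2 clash with Table 3 needs a symptom that is both unexplained and judged at least possibly drug-related. Cough is among the most frequent perindopril reactions, and a cough put down to perindopril is arguably explained. The case is narrow, though it can occur.

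**Conclusion.** The point holds for Section 7.5 against Table 3. For drug-related gastrointestinal perforation or fistula, and a little less sharply for wound dehiscence, the protocol gives differing instructions at every grade and no order of precedence. The respiratory mismatch is real but secondary. Section 5.2.1 is incomplete on these events, not opposed to Section 7.5.

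The conclusion assumes that the event is judged related to study drug, since otherwise Table 3 does not apply, and that Table 3 and its footnotes are complete as they appear in the document.

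Two further inferences should be resisted. The documents give no rate for these events in this population, so no expected number of patients can be stated. Nor does the inconsistency create a counting problem in the Section 8.1 summaries: these tabulate the dose changes, interruptions and withdrawals that took place, with reasons, so a patient is counted by what was done. Alpha, power, sample size and the primary analysis do not change.

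This is an inconsistency of text that should be corrected because it concerns a safety instruction. This review takes no position on which clinical rule is right.

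**What to change.** Reconcile Section 7.5 and Table 3 so that perforation or fistula, wound dehiscence and unexplained respiratory symptoms each have one instruction. This could be done by a Table 3 footnote that cross-refers to Section 7.5, or by amending Section 7.5. State which passage prevails if they differ. The sponsor's clinicians choose which rule stands.

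Align Section 5.2.1 only for an event that the clinicians decide is a permanent stop. Adding all three events to that list would not be safe editing, because it would turn the conditional respiratory hold into mandatory withdrawal and so set up a new conflict with Section 7.5.

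The cost is a footnote or a few amended sentences, plus any matching entry in Section 5.2.1. No procedure, visit, data item or analysis is added.

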7.5.1 Adverse events

7.5.1.1 Definitions

Definition of adverse event (AE)

In a clinical study, an AE is any untoward medical occurrence (i.e. any unfavorable and unintended sign [including abnormal laboratory findings], symptom or disease) in a patient or clinical investigation subject after providing written informed consent for participation in the study. Therefore, an AE may or may not be temporally or causally associated with the use of a medicinal (investigational) product.

Surgeries and/or procedures are not Adverse Events – they are therapeutic measures for conditions that require such intervention. However, the condition requiring surgery may be an Adverse Event. Therefore, if surgical procedure is reported, the basic condition leading to surgery is entered as event respectively.

Disease progression in itself should not be reported as an AE. However, if disease progression results in events that fit AE definition, these should be reported as such.

In the following differentiation between medical history and AEs, the term “condition” may include abnormal physical examination findings, symptoms, diseases, laboratory, or ECG.

- Conditions that started before signing of informed consent and for which no symptoms or treatment are present until signing of informed consent are recorded as medical history (e.g. seasonal allergy without acute complaints).

Phase II Study of Perindopril and Regorafenib in mCRC (PARICCA)

- Conditions that started before signing of informed consent and for which symptoms or treatment are present after signing of informed consent, at *unchanged intensity*, are recorded as medical history (e.g. allergic pollinosis).
- Conditions that started or deteriorated after signing of informed consent will be documented as adverse events.

In this study, investigators should also report signs and symptoms that are associated with progressive disease or the worsening of the existing cancer, and avoid using the AE term progressive disease.

Definition of serious adverse event (SAE)

An SAE is classified as any untoward medical occurrence that, at any dose, meets any of the following criteria (a – f):

a. Results in death

b. Is life-threatening

The term ‘life-threatening’ in the definition refers to an event in which the patient was at risk of death at the time of the event, it does not refer to an event which hypothetically might have caused death if it were more severe.

c. Requires inpatient hospitalization or prolongation of existing hospitalization

A hospitalization or prolongation of hospitalization will not be regarded as an SAE if at least one of the following exceptions is met:

- The admission results in a hospital stay of less than 12 hours
- The admission is pre-planned (i.e. elective or scheduled surgery arranged prior to the start of the study)
- The admission is not associated with an AE (e.g. social hospitalization for purposes of respite care).

However, it should be noted that invasive treatment during any hospitalization may fulfill the criterion of ‘medically important’ and as such may be reportable as an SAE dependent on clinical judgment. In addition, where local regulatory authorities specifically require a more stringent definition, the local regulation takes precedence.

d. Results in persistent or significant disability / incapacity. Disability means a substantial disruption of a person’s ability to conduct normal life’s functions.

e. Is a congenital anomaly / birth defect

f. Is a medically important event as judged by the investigator

Phase II Study of Perindopril and Regorafenib in mCRC (PARICCA)

Investigators should also report any sign and symptom of progressive disease or worsening of the existing cancer as a separate SAE if the "serious" criteria are met. Investigators should avoid reporting progressive disease as the AE term.

All of the following events are to be reported to the sponsor as SAEs following the reporting instructions:

- Acute myeloid leukemia (AML)
- myelodysplastic syndrome (MDS) occurring after chemotherapy for cancer
- Additional primary cancers (including skin cancers) regardless of relationship to study treatment

A Serious Adverse Event should be described as "Death" when the cause of death is unknown; otherwise "Fatal" must be entered as the outcome of the Adverse Event and/or reason for seriousness.

All adverse events must be assessed by the investigator for severity and seriousness.

7.5.1.2 Classifications for adverse event assessment

CTCAE v4.03 criteria will be used for evaluation during the trial.

The incidence of HFSR will be expressed as the number of patients out of study (N=34) who are experiencing HFSR of all grades. Severity will be evaluated using CTCAE v4.03 criteria.

The incidence of hypertension will be expressed as the number of patients on study (N=34) who are experiencing hypertension of all grades. Severity will be evaluated using CTCAE v4.03 criteria.

All AEs will be assessed and documented by the investigator according to the categories detailed below.

